## Demographic Characteristics of Study Sample Required for Clinical Trials

	Baseline A	Intervention	Baseline B	Totals
Enrolled	63	50	14	127
Completed	62	47	13	122
Lost to Follow-up	1	3	1	5
Under 18 Years of Age	0	0	0	0
Between 18 and 65	37	26	10	73
Over 65	26	24	4	54
Female	28	21	6	55
Male	35	29	8	72
American Indian, Alaskan	5	6	2	13
Asian	0	0	0	0
Hawaiian or Islander	1	0	0	1
Black or African American	0	0	0	0
White	56	43	11	110
More than one race	0	0	0	0
Unknown or Not Reported	1	1	1	3
Subtotal	63	50	14	127
Hispanic or Latino	0	0	0	0
Not Hispanic or Latino	61	47	11	119
Unknown or Not Reported	2	3	3	8
Subtotal	63	50	14	127

In addition, Table 3 presents the number of patients excluded by criterion and Table 4 shows the number of patient enrolled in the study from each county by experimental condition.

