**Table 3**

**Number of Patients Excluded by Criteria**

Exclusion Criteria	Number of Patients
Age	242
Not an Inpatient	41
Substance Abuse – Mental Illness	65
Prisoner	29
Extended Care Facility	12
Not Going Home	26
Extended Observation	28
Cognitive Impairment	24
Actively Dying	16
Other	65
Total	570

Table 4  
Participants by County

	Baseline	Intervention	Baseline	Total
Sanders	10	21	4	35
Beaverhead	8	8	0	16
Powell	11	6	2	19
Lake	34	15	8	57
Total	63	50	14	127

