Researchers prepared an evaluation package that included the three-item Care Transition Measure (Coleman, Mahoney, & Parry, 2005), the 12 item Short Form of the Medical Outcome Study (Stewart and Ware, 1992), and a Rural Transitions Measure (RTM14; Montana Team, 2016). The RTM14 asked patients to report whether they strongly agree, agree, disagree, or strongly disagree with each of 14 statements reflecting services provided after discharge to facilitate an effective transition home. Researchers also asked patients to report the number of times that they had seen a PCP, visited an emergency department of any hospital, been admitted to SPH, or been admitted to any other hospital since they were discharged or since their last report.

**Data collection.** We asked patients to complete the instruments in the evaluation package at 3, 7, 14, 21, 30, 60, and 90 days after they were discharged from the RRH. RTCs gave patients the 3 and 7 day evaluation packages in the RRH to complete at home. The research staff mailed the remainder of the evaluation packages to patients three days before the end of each measurement period. Each evaluation package included an instrument and a

self-addressed stamped envelope for returning a completed questionnaire. In addition, the first six instruments included a \$10 honoraria and the last packet included a \$40 honoraria.

Finally, we used information in the Epic® patient records to collect demographic data and information on emergency department visits, outpatient admissions, and hospitalizations at the participating hospitals. Finally, RTCs and LCTC kept notes detailing the patient situation and experiences that were posted in the EOC tab in Epic®.

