  - b) We will use a repeated measures ANOVA model (over the 7 time periods) to model the SF-12 Physical Health score as a function of treatment group.
- 5) Mental Health as measured by the Short Form (SF12) Mental Health Score
- a) Hoi: There is no difference in mean SF-12 Mental Health scores between the standard and enhanced discharge groups (null hypothesis); H1i: The mean SF-12 Mental Health scores differ between the standard and enhanced discharge groups.
  - b) We will use a repeated measures ANOVA model (over the 7 time periods) to model the SF-12 Mental Health score as a function of treatment group.
- 6) Care Transition Measure (CTM3) of discharge coordination services
- a) Hoi: There is no difference in mean CTM3 scores between the standard and enhanced discharge groups (null hypothesis); H1i: The mean CTM3 scores differ between the standard and enhanced discharge groups.
  - b) We will use a repeated measures ANOVA model (one time period at 3 days post discharge) to model to assess these hypotheses.
- 7) Rural Transition Measure (RTM14) of the delivery of transition services and supports
- a) H0: There is no difference in the mean RTM14 score between the standard and enhanced discharge groups (null hypothesis); H1: Patients in the enhanced discharge group will have a higher mean RTM14 rating than patients in the standard discharge group.
  - b) We will use a repeated measures ANOVA model (over the 6 time periods) to model the RTM14 score as a function of treatment group.

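### SF-12 and RTM14: the planned repeated measures ANOVA leaves open what happens to patients with unreturned forms and does not adjust for county or period (minor)

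*Combined protocol and SAP*

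**What the plan says.** Statistical Analysis Plan items 4b, 5b and 7b give one sentence per outcome:

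- SF-12 physical: "repeated measures ANOVA model (over the 7 time periods) to model the SF-12 Physical Health score as a function of treatment group".
- SF-12 mental: "repeated measures ANOVA model (over the 7 time periods) to model the SF-12 Mental Health score", again by treatment group.
- RTM14: "We will use a repeated measures ANOVA model (over the 6 time periods", by treatment group. The six waves are not named.

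None of the three states an estimation method, a covariance structure, a group-by-time term, an analysis set, covariates or a rule for unreturned forms.

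Under Data collection, forms were due "at 3, 7, 14, 21, 30, 60, and 90 days after they were discharged from the RRH". The day 3 and day 7 packages were handed over in hospital for completion at home. For the later ones, "The research staff mailed the remainder of the evaluation packages to patients three days before the end of each measurement period". Each package held a "self-addressed stamped envelope for returning a completed questionnaire". The same section gives a payment with every form: $10 with each of the first six and $40 with the last.

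Table 2 lists 127 enrolled, 122 completed and 5 under "Lost to Follow-up". It does not say whether completed means every form returned or only not lost. No return rate by wave appears.

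The Design section describes non-randomised conditions, introduced county by county over time, with a final return to baseline. Table 4, "Participants by County", gives the resulting county mix.

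**The concern.** The same SAP sentence covers analyses that treat unreturned forms differently. In the wide-format (multivariate) repeated measures procedure, each patient is one row and a row with any empty wave is discarded. A long-format univariate ANOVA, or a likelihood mixed model, uses whatever forms came back. With seven home-completed waves these can use quite different numbers of patients, and they can give different answers from the same data.

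At stake are a choice of analysis that the SAP leaves open and, possibly, precision. Separately, a model in treatment group alone compares conditions that differ in county mix and in time of enrolment, although county, LACE+ and PAM were recorded for use as covariates.

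**Working it through.** The documents state no power, SD, effect size or return rate for these outcomes, so there is no planned figure to reproduce. The counts agree: 63 + 50 + 14 = 127 enrolled, 62 + 47 + 13 = 122 completed, 1 + 3 + 1 = 5 lost.

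**1. Near-zero end (Table 2).** Suppose completed means every form returned. The wide-format fit then loses 127 − 122 = 5 patients. With independent misses this corresponds to a return of (122/127)^(1/7) = 0.994 per wave and a standard-error ratio of 1.02. If those 5 returned no form, neither method can use them and the ratio is 1.00.

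**2. Lower returns (assumed).** Let p be the return per wave and k the number of waves.

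- Independent misses: patients kept = 127 × p^k. For example, 127 × 0.90^7 = 60.7 and 127 × 0.90^6 = 67.5 (67.49).
- Clustered misses: beta-binomial with correlation c = 0.3, a = p(1−c)/c, b = (1−p)(1−c)/c; patients kept = 127 × B(a+k, b)/B(a, b).
- Standard-error ratio, wide-format fit over a fit using all returned forms: √{ Σ P(m)·v(m) / [P(k)·v(k)] }, where m is the number of forms returned, v(m) = m/(1 + (m−1)r), and r is the within-patient score correlation, assumed 0.6.
- Example, 7 waves, 90%, independent: v(7) = 7/4.6 = 1.522; Σ P(m)·v(m) = 1.505; P(7) = 0.478; ratio = √(1.505/0.728) = 1.44.

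| Waves | Return per wave | Kept, independent | Ratio | Kept, clustered | Ratio |
|---|---|---|---|---|---|
| 7 | 95% | 89 | 1.19 | 106 | 1.09 |
| 7 | 90% | 61 | 1.44 | 87 | 1.19 |
| 7 | 80% | 27 | 2.16 | 58 | 1.44 |
| 6 | 95% | 93 | 1.16 | 107 | 1.08 |
| 6 | 90% | 67 | 1.36 | 90 | 1.18 |
| 6 | 80% | 33 | 1.92 | 62 | 1.39 |

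The score correlation matters little: for r from 0.4 to 0.8, the 7-wave, 80%, independent ratio runs from 2.13 to 2.17.

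**3. Direction of bias.** Loss to follow-up was 3/50 in intervention and 2/77 in baseline (Fisher two-sided p = 0.38). An illustrative simulation used 77 against 50 patients, 7 waves, SD 10, true difference 0 and later-wave returns of about 94% or 89%. The complete-case bias was 0.0 and 0.0 when return depended on score equally in both conditions. It was −1.1 and −2.0 when only the standard group's return depended on score, and +1.1 and +2.0 when only the enhanced group's did. The sign therefore follows from an assumption that the documents do not supply.

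**4. County (Table 4).** Sanders supplies 21/50 of intervention and 14/77 of baseline patients (0.420 − 0.182 = 0.238). Lake supplies 15/50 and 42/77 (0.300 − 0.545 = −0.245). The unadjusted contrast thus moves by about 0.24 points for each point by which Sanders differs from the other counties, and by about 0.25 the other way for Lake.

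Cost of adjusting: the within-county information Σ n₁n₀/N is 21·14/35 + 8·8/16 + 6·13/19 + 15·42/57 = 27.56, against 50·77/127 = 30.31 unadjusted. The standard-error factor is √(30.31/27.56) = 1.049.

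Enrolment by county and calendar period is not tabulated, so the cost of a period term cannot be computed.

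**The case against.** The strongest reply has four parts.

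- **Repeated measures ANOVA need not mean deletion.** This stands. A univariate split-plot fit in long format keeps returned waves, and some analysts use the term for a mixed model. A reader might infer that the SAP commits to dropping every patient with a missing form. It does not: deletion follows from one procedure, and the SAP names none.
- **The loss may be close to nil.** This stands too. Table 2 shows 122 of 127 completed, and every form carried a payment. The 80% rows, above all with independent misses, are the pessimistic end of an assumed range.
- **Bias has not been shown.** Correct. A reader might infer that selective return tilts the comparison. No text describes form handling that differs by condition, 3/50 against 2/77 supports no direction, and equal score dependence gives no bias. The simulated values rest on SD 10 and 7 waves and do not carry over to RTM14.
- **County is a different problem from missing forms, and county alone does not meet it.** Partly right. Both concern the same three model sentences, so they can be mended together. But condition is also tied to calendar time, so a period term is needed where it can be estimated.

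What remains is that the wording leaves the handling of unreturned forms open and the contrast unadjusted in a non-randomised design.

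**Conclusion.** The point holds as a minor one. What is certain is that items 4b, 5b and 7b do not say how patients with unreturned forms are treated, and that they model score on treatment group alone. What is only possible is a loss of precision under a wide-format fit. For 7 waves this runs from nothing (ratio 1.00 to 1.02) to a ratio of 2.16 at 80% return with independent misses, or 1.44 with clustered misses. Those larger values rest on assumed return rates, a score correlation of 0.6 and, for clustering, a correlation of 0.3. No direction of bias can be claimed. The SAP calls these outcomes intermediary; the hospitalisation and emergency department analyses are not affected.

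**What to change.** In 4b, 5b and 7b, replace the ANOVA with a REML mixed model for repeated measures:

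- Terms: condition, visit and condition-by-visit, on all patients with at least one returned form. Contrast: the condition difference averaged over visits.
- Covariance: unstructured (28 parameters for 7 waves, 21 for 6), with a stated simpler fallback, such as a patient random intercept with correlation decaying over days since discharge.
- Covariates: county and LACE+, PAM if feasible, and calendar period of enrolment where estimable.
- Reporting: define completed, name the six RTM14 waves, and give returns by wave and condition, including patients with no form.
- Sensitivity: a missing-not-at-random analysis, for example imputing and then shifting the missing scores by condition until the conclusion changes.

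Enrolment and completion are already reported, so date the change and label it as made after data collection.

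Cost: SAP wording and standard software, with no new data. The downsides are slightly more analysis work, possible convergence problems (hence the fallback) and reliance on missing at random (hence the sensitivity analysis). Patients with no returned form are lost either way. County adjustment costs about 5% in standard error before any gain from explained variance, and a period term costs more. With complete data and no covariates, the averaged contrast equals the difference in patient means that the ANOVA group test uses, so little is given up if returns were high.
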